# A

## Objectives

- List the objectives to correspond directly with the listed hypotheses:

**Aim 1:** To compare the performances of hyperaroused PI sufferers and normally alert normal sleepers across a battery of computer-administered neuro-cognitive reaction time tests.

**Aim 2:** To examine the relative sensitivities of a range of simple and complex reaction time tests for discriminating PI sufferers from non-complaining normal sleepers.

**Aim 3 (Exploratory):** To examine the degree to which measures of the macro- and micro-architecture of sleep account for the daytime performance deficits shown by hyperaroused PI sufferers

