## Study Design/Clinical Plan

- Provide a concise overview stating the type of experimental design

This study will use a matched-groups cross-sectional experimental design. Age and gender matched groups of hyperaroused PI sufferers and non-complaining normal sleepers (NS) will be recruited and enrolled. A comprehensive screening process that includes structured sleep and psychiatric interviews, screening questionnaires, vitals, urine pregnancy test, medical history, and diagnostic PSG will be used to determine eligible subjects. Our screening procedures and selection criteria are designed to allow us to identify and enroll hyperaroused PI sufferers and normally alert normal sleepers. PI sufferers enrolled will meet Research Diagnostic Criteria for insomnia disorder, score  $> 14$  on the Insomnia Severity Index, report insomnia for  $> 3$  months, have sleep difficulties  $\geq 3$  nights per week, score  $\leq 3$  on the Epworth Sleepiness Scale (ESS), score  $\geq 29$  on the Hyperarousal Scale and report an inability to nap in the daytime. The normal sleepers enrolled will report general satisfaction with sleep and no sleep/wake complaints, score  $\leq 10$  on the ESS, score  $< 25$  on the Hyperarousal Scale, and deny a practice of routine daytime napping. Those excluded will have: (a) a sleep-disruptive medical condition (e.g., rheumatoid arthritis); (b) a current major psychiatric (Axis I) condition on the basis of a Structured Clinical Interview for Psychiatric Disorders (SCID); (c) sedative hypnotic dependence and unwillingness/inability to abstain from these medications while in the study; (d) use of anxiolytics, antidepressants, or any other psychotropic medication; or (e) an apnea/hypopnea index (AHI)  $> 5$  or a periodic limb movement-related arousal index  $> 15$  during on screening PSG that includes a full sleep montage to allow for detection/diagnosis of sleep-disordered breathing and PLMD. Additionally, self-described NS who meet criteria for any sleep disorder and those insomnia sufferers who meet criteria for a comorbid sleep disorder in addition to PI will also be excluded.

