# A

factorial analysis. Although our statistical model could also include "trials" as a factor, we have chosen to limit the complexity of our analyses by excluding this factor and using mean values of each of our performance measures across trials for each participant in our analyses. To further simplify our analyses we will compute mean values of our 5 dependent measures for the three simple tests and another set of mean values of these dependent measures for our three complex tests and use those composite means in all planned analyses.

Before conducting tests of the study hypotheses, we will conduct a number of preliminary 2 (PI vs. NS) x 2 (alert vs. sleepy) x 2 (simple vs. complex test) ANOVAs and cross tabs analyses to determine if the various "cells" of our study include participants who do not differ significantly in terms of their mean ages, years of education, gender compositions and racial/ethnic compositions. If study "cells" are found to differ significantly on any of these variables, those variables will be used as covariates in statistical models designed to test study hypotheses. If study cells do not differ in regard to these variables we will use unadjusted statistical models to test study hypotheses.

For study hypotheses 1 & 2, we will conduct 2 (PI vs. NS) x 2 (simple vs. complex test) MANOVAs/MANCOVAs analyses to test for statistical significance across the multiple performance measures derived from the neuro-cognitive test battery. If the MANCOVA/MANOVA shows significant results, univariate ANCOVAs/ANOVAs will be conducted to tests for similar significant effects for each individual performance measure (i.e., mean reaction time; within subject standard deviations for reaction time; error responses).

Hypothesis 1 will be tested via examination of the main effect of the *group factor* (PI vs. NS) in these analyses. Findings showing significantly slower and more variable reaction times, fewer correct responses and higher error rates in the hyperaroused PI group will support this hypothesis. Elimination of these statistical differences in repeat analyses that use hyperarousal scale scores as a covariate will confirm the role of hyperarousal in explaining the observed group differences.

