Hypothesis 2 will be tested via examination of the interaction of the *group factor* (PI vs. NS) and *test difficulty factor* (simple vs. complex) in these analyses. This finding coupled with a posteriori comparisons showing that PI participants have significantly poorer performances than do NS only on the complex tasks will support this hypothesis. Again, elimination of these statistical differences in repeat analyses that use each participant's hyperarousal scale score as a covariate will confirm the role of hyperarousal in explaining the observed group differences on complex tasks.

Our Exploratory Aim will require us to derive a variety of measures from the PSGs conducted on the two nights preceding daytime testing. Following the AASM Scoring Manual guidelines we will score these PSG records and obtain measures of total sleep time, sleep onset latency, wake time after sleep onset, sleep efficiency, and percentages of stages N1, N2, N3, and R for each night. We also will de-artifact each night and then perform a Fast Fourier Transform and subsequent sleep EEG spectral analysis as per our previously published reports to derive NREM absolute and relative spectral power measures in the delta, theta, alpha, sigma, beta and gamma bandwidths. Once these measures are derived for each night, we will compute mean values of these measures for the two PSG nights and then enter those into multivariate regression analyses to determine which measures predict each of the five performance variables used as dependent measures. Those found to be predictive of performance indices will be entered as covariates in the above factorial analyses to determine if any such measures account for the anticipated relative deficits shown by the insomnia group vis a vis the normal group. Since we will anticipate group differences only on the 5 performance measures derived from the set of complex tests, we will plan to test our sleep measures as covariates only in one-way group comparisons using response latency, correct response rate, and error rate data acquired from the complex tests as dependent measures in these analyses. We, thus, will conduct and 5 ANCOVA analyses in which the sleep measures are tested as covariates with each of the 5 performance measures obtained from the complex reaction time tests.

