In addition to these analyses, we will conduct simple bi-variate correlational analyses as well as multi-variate regression analyses to examine the association between the EEG measures and subjects' scores on the hyperarousal scale. In regression analyses hyperarousal scores will be predicted by the various measures derived from conventional and spectral scoring of the PSG records.

These analyses could provide important new information about the relationship between nighttime sleep and daytime performance. Specifically these analyses could help identify specific aspects of the macro and micro-architecture of sleep that are markers for sleep-disruptive hyperarousal and produce impairment in daytime neuro-cognitive performance. These sleep measures therefore could be considered important targets for insomnia therapies to address in optimizing the types of neuro-cognitive endpoints studied herein. Such findings would seem of great interest to Merck and other

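### The Aim 3 sleep-performance regressions and five ANCOVAs specify no age or gender term, so age- or gender-confounded sleep measures may be selected and, where they also differ between groups, may distort the PI-NS deficit

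*Combined protocol and SAP*

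**What the plan says.** Aim 3 is labelled exploratory. Its purpose, under Objectives, is "To examine the degree to which measures of the macro- and micro-architecture of sleep account for the daytime performance deficits" seen in hyperaroused PI sufferers. The Statistical Plans section carries it out in two steps.

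- **Selection.** Two-night means of the conventional and spectral sleep measures are computed, and the plan will "enter those into multivariate regression analyses to determine which measures predict each of the five performance variables used as dependent measures".
- **Adjustment.** "Those found to be predictive of performance indices will be entered as covariates in the above factorial analyses". This is then narrowed to one-way group comparisons on the complex tests: "5 ANCOVA analyses in which the sleep measures are tested as covariates with each of the 5 performance measures".

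The only terms named are the sleep measures and, in the second step, group.

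Two other provisions bear on age and gender. Under Study Design/Clinical Plan, "Age and gender matched groups of hyperaroused PI sufferers and non-complaining normal sleepers (NS) will be recruited and enrolled". Earlier in Statistical Plans, the cells are compared on age, education, gender and race/ethnicity. If they differ significantly, "those variables will be used as covariates in statistical models designed to test study hypotheses"; otherwise, "If study cells do not differ in regard to these variables we will use unadjusted statistical models to test study hypotheses".

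The closing paragraphs of Statistical Plans say that these analyses could help identify features of sleep that mark hyperarousal and "produce impairment in daytime neuro-cognitive performance", and that such features could be considered targets for insomnia therapies.

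**The concern.** Matching balances age and gender between PI and NS. It does not make everyone the same age. The slope of performance on a sleep measure is estimated across people of different ages and both genders, and the documents give no age range that would limit this variation. If age is related to both the sleep measure and performance, the slope is confounded within each group, and a group term does not remove that.

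The conditional covariate rule looks for something else. It tests whether groups differ on age, not whether age is related to sleep and performance within groups. The better the matching works, the less likely the rule is to bring age in.

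Two results are at stake: which sleep measures are called predictive, and how much of the PI-NS deficit each is said to account for. The second is affected only for measures that also differ between the groups. Those are the measures Aim 3 is looking for, since a measure with no group difference cannot account for a group deficit.

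**Working it through.** **Inputs from the documents (Power Considerations).** 82 per group; alpha .05, taken as two-sided because sidedness is not stated; complex-test latency 496.65 (PI) and 438.14 (NS) msec, SD 133.4.

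**The plan's own figure.** The difference is 496.65 − 438.14 = 58.51 msec, and 58.51/133.4 = 0.4386 SD. Power is about Φ(0.4386 × √(82/2) − 1.96) = Φ(2.808 − 1.96) = 0.80, as stated. The documents give no figure for Aim 3, so 58.51 msec is used below as the deficit to be explained.

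**Assumptions, not in the documents.** Age has the same correlation r with the sleep measure and with latency within groups, for r = .2, .3, .4 and .5. The sleep measure has no effect of its own on latency. The groups are pair-matched on age. One sleep measure is considered at a time. The PI-NS difference in that measure is 0, +0.5 or −0.5 SD.

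**Step 1: false selection.** The sleep measure and latency then correlate at r × r within groups, entirely through age. By Fisher's z with the group term included, the chance of p < .05 is about Φ(atanh(r²) × √160 − 1.96), plus a negligible opposite tail (0.7 percentage points at r = .2, less above). Simulation used 4,000 trials per setting, with no group difference in the sleep measure.

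| r | r² | Fisher approximation | Simulated, sleep measure alone | Simulated, age added |
|---|---|---|---|---|
| .2 | .04 | 8% | 8% | 5% |
| .3 | .09 | 21% | 20% | 6% |
| .4 | .16 | 53% | 51% | 5% |
| .5 | .25 | 90% | 88% | 5% |

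**Step 2: effect on the group difference.** Change in the adjusted PI-NS difference = within-group slope × PI-NS difference in the sleep measure = (133.4 × r²) × shift.

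- Shift 0, a measure that merely tracks age: the change is 0. In simulation the difference is 58–59 msec before and after adjustment at every r.
- Shift +0.5 SD:

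| r | 133.4 × r² × 0.5 (msec) | Share of 58.51 | Simulated adjusted difference (msec) | With age added (msec) |
|---|---|---|---|---|
| .2 | 2.67 | 4.6% | 55.6 | 58.3 |
| .3 | 6.00 | 10.3% | 52.2 | 58.3 |
| .4 | 10.67 | 18.2% | 48.2 | 58.9 |
| .5 | 16.68 | 28.5% | 41.8 | 58.4 |

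- Shift −0.5 SD: the same amounts are added to the deficit. At r = .5 the adjusted difference is 74.7 msec, and it returns to 58.0 with age in the model.

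**Step 3: why the selection regression also needs a group term.** With a shift of ±0.5 SD and age in the model but no group term, a measure with no effect of its own is still selected in about 10% to 15% of trials, because it stands in for group. With both age and group the rate is about 5%.

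**The case against.** **A measure that merely tracks age cannot explain the deficit.** A reader might infer that any age-related sleep measure will be reported as accounting for part of the PI-NS difference. The documents do not support that. The groups are to be age- and gender-matched, so such a measure has no expected group difference, and adjusting for it removes nothing. This objection stands in full: distortion of the deficit is limited to measures that differ between groups for some further reason, and it can go either way.

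**The rates describe one measure at a time.** The plan lists 8 conventional measures plus absolute and relative power in 6 bands, 20 in all, and its wording may mean joint entry. If all measures track age equally, the age signal is split among them. A simulation of joint entry (group term included, r = .2/.3/.4/.5) gave per-measure rates of 7/10/15/20% for 8 independent measures, 6/7/8/8% for 20 independent measures, and about 5% throughout for 20 measures with residual correlation .5. This stands as a limit on the selection rates. It does not remove the distortion of the group difference if all the measures are kept.

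**The covariate rule may reach the ANCOVAs.** The selected measures enter the factorial analyses to which that rule applies, so age or gender could be added there. It is therefore too strong to say that these models will carry no such term. The rule is still triggered by group imbalance rather than within-group confounding, and it does not mention the regressions. It could also miss some imbalance: with 82 per group, an age difference up to 1.975/√41 = 0.31 SD would not be significant.

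**The sizes are assumed and the stakes are low.** The documents give no age range, age correlation or PI-NS difference in any sleep measure, and nothing in them favours .5 over .2. Gender works by the same route but has not been quantified. Aim 3 is exploratory and the talk of therapy targets is hedged. All of this stands, and it limits the weight of the point rather than removing it.

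**Conclusion.** The point holds in limited form. As written, the Aim 3 models specify no age or gender adjustment, and neither matching nor the conditional rule protects the sleep-performance slopes from confounding within groups. A sleep measure related to performance only through age or gender may be selected as predictive. If it also differs between PI and NS for another reason, it can wrongly shrink or inflate the deficit.

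Under the stated single-measure assumptions, false selection runs from about 8% to 88% instead of 5%, and distortion from about 5% to 29% of the deficit for a 0.5 SD group difference. These are illustrations over an assumed range, not predictions for this study; joint entry may bring the per-measure selection rate close to nominal. Hypotheses 1 and 2, the sample size and the power figures do not depend on this. It is a free improvement with low stakes.

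**What to change.** In the exploratory-aim paragraph of Statistical Plans, state that age and gender enter as fixed covariates in every Aim 3 regression, together with a group term, and in each of the five ANCOVAs, whether or not the groups differ on them. Add that a sleep measure will be described as predicting performance, or as accounting for the deficit, only on the adjusted estimate. For the second claim, compare the group difference with and without the sleep measure, keeping age and gender in both models.

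The cost is a sentence or two of analysis text and two degrees of freedom out of about 160 in each model, plus one for group in the regressions. Age and gender are already collected for matching, so no new data are needed.

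### The Aim 3 sleep-measure screen mentions no group term, so a measure that only differs between PI and NS is over-selected and can be wrongly credited with explaining the deficit

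*Combined protocol and SAP*

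**What the plan says.** Statistical Plans derives eight conventional PSG measures ("total sleep time, sleep onset latency, wake time after sleep onset, sleep efficiency, and percentages of stages N1, N2, N3, and R") and twelve spectral ones ("NREM absolute and relative spectral power measures in the delta, theta, alpha, sigma, beta and gamma bandwidths"), and averages each over the two nights. The next step is to "enter those into multivariate regression analyses to determine which measures predict each of the five performance variables used as dependent measures". Sleep measures are the only predictors named. No entry threshold is given, and nothing is said about group or about fitting within groups.

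The hits are then carried forward: "Those found to be predictive of performance indices will be entered as covariates in the above factorial analyses". The stated purpose is "to determine if any such measures account for the anticipated relative deficits shown by the insomnia group vis a vis the normal group". The closing lines of the same paragraph narrow this to the complex tests: "we will plan to test our sleep measures as covariates only in one-way group comparisons". So group is in the second-stage model, and there are five such models.

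For the hyperarousal score, the same section treats disappearance of the significant difference as confirmation of its role. It gives no corresponding criterion for the sleep measures. Objectives and Hypothesis both frame Aim 3 as a question of how far sleep measures account for the deficit.

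**The concern.** Study Design/Clinical Plan recruits two contrasting groups: PI with an Insomnia Severity Index above 14 and a Hyperarousal Scale score of at least 29, and NS satisfied with their sleep and scoring below 25. Sleep measures may well differ between such groups, and Hypothesis 1 predicts that performance does. In a regression that omits group, any sleep measure that differs by group is then associated with performance through group membership alone.

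Such a measure enters the second stage as a candidate explanation, chosen in the same data. It is correlated with group, so it widens the standard error of the group difference. Selection also tends to pick samples in which the adjusted difference happens to shrink. Either can make a real deficit look explained. Statistical Plans hopes the analyses might point to features of sleep that are "markers for sleep-disruptive hyperarousal and produce impairment in daytime neuro-cognitive performance" and that therapies could target, so a false attribution would have consequences.

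**Working it through.** **1. Inputs and the plan's own figure.** Power Considerations gives complex-test latency of 496.65 (PI) and 438.14 (NS) msec, SD 133.4, 82 per group, alpha .05, power .80.

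- d = (496.65 − 438.14)/133.4 = 58.51/133.4 = 0.439.
- d/√(2/82) = 2.81, and Φ(2.81 − 1.96) = .80 two-sided. The stated figure reproduces.

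This is the only complex-test effect in the plan, and Aim 3 concerns the complex tests. The plan gives no PI-NS difference for any sleep measure, so the values of d_s below are assumptions, as is a screening threshold of p < .05.

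**2. Size of the screen.** 8 + 12 = 20 measures; 20 × 5 outcomes = 100 pairs. With no true relation, 20 × .05 = 1 false hit is expected per outcome and 5 over all pairs. With independent tests, the chance of at least one is 1 − .95^20 = .64 per outcome.

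**3. Selection of a measure unrelated to performance within group.** Let it differ between groups by d_s SD. Without a group term, the correlation across all 164 participants is

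r = (d × d_s/4) / √[(1 + d²/4)(1 + d_s²/4)].

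With z = atanh(r) × √161, the chance of p < .05 is Φ(z − 1.96) + Φ(−z − 1.96).

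| d_s | r | z | Selected, formula | Selected, simulation | With group in the model |
|---|---|---|---|---|---|
| 0.5 | .052 | 0.66 | .10 | .09-.11 | about .05 |
| 1.0 | .096 | 1.22 | .23 | .24 | about .05 |
| 1.5 | .129 | 1.64 | .37-.38 | .37-.38 | about .05 |

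**4. What the second stage does with it.** The ANCOVA contains group, so a covariate fixed in advance with no within-group slope does not bias the group coefficient. It does multiply its standard error by √(1 + d_s²/4): 1.12 at 1.0 SD and 1.25 at 1.5 SD. Power for the complex-test difference falls from .80 to Φ(2.81/1.12 − 1.96) = .71 and Φ(2.81/1.25 − 1.96) = .61, with no mechanism at work.

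Selection in the same data adds some bias. In simulated trials with a significant unadjusted difference and a selected null measure, the adjusted difference averaged 0.87, 0.82 and 0.81 of the unadjusted one (d_s = 0.5, 1.0, 1.5). The chance that one such measure is both selected and removes significance, given a significant unadjusted difference, was 1.9%, 7.7% and 17.6%.

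**5. All 20 measures screened jointly, none related to performance within group.** False elimination means that the group p-value moves from below .05 to .05 or above.

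| Measures differing | d_s | Correlation among measures | Screen without group | Screen with group |
|---|---|---|---|---|
| 5 | 0.8 | 0.3 | 15% | 6% |
| 10 | 0.8 | 0 | 24% | 10% |
| 10 | 0.8 | 0.3 | 18% | 9% |
| 5 | 1.2 | 0 | 24% | 9% |
| 5 | 1.2 | 0.3 | 22% | 10% |

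Over all settings with 5 or 10 measures differing by 0.5-1.2 SD, and over repeat simulations, the range is about 8-27% without group and 4-13% with it. When no measure differs, it is about 2-4% without group. Screening one measure at a time widens the range without group to 10-59%; with group it is 4-13%. With group in the screen, the average adjusted difference stays at 0.98-1.02 of the unadjusted one.

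**The case against.** The strongest reply is that the plan is silent rather than wrong. A reader might infer that it specifies a combined-sample screen without group. It does not say so: that is the natural reading, because sleep measures are the only predictors named and group first appears at the covariate stage. If a group term was intended, one sentence settles the matter.

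A reader might also infer that measures that merely mark group will be declared the explanation. The documents do not support that. The second-stage model contains group, and under joint regression the significant deficit survives in most simulated trials.

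Nor is loss of significance the stated rule here. It is stated for the hyperarousal score only, so the elimination rates above show what would happen if that rule were carried over. They do not describe a rule the plan sets for sleep measures.

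The sleep-measure differences are assumed. PI entry rests on interview and self-report rather than PSG sleep values, and Background and Rationale mentions PI sufferers with normal objective sleep duration, so small differences are possible. The plan's language about treatment targets is conditional, and the aim is labelled exploratory.

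All of this limits the size and certainty of the concern. It does not justify a screen that, followed as written, favours markers of group membership when a nearly free alternative does not.

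**Conclusion.** The concern holds as a conditional one about exploratory Aim 3. Followed as written, the screen selects a measure that only differs between groups about 10%, 24% or 38% of the time (0.5, 1.0, 1.5 SD) instead of 5%. With 5 or 10 of 20 such measures, a significant deficit is falsely eliminated in roughly 8-27% of trials under joint regression, against about 2-4% when none differ.

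These sizes rest on the plan's d = 0.439, on assumed group differences and correlations among the sleep measures, on a .05 threshold, and on reading significance loss as explanation. Independently of those assumptions, the plan asks for a degree of explanation and names no quantity to measure it. Hypotheses 1-2 and the sample size are unaffected.

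**What to change.** - Include group as a term in every Aim 3 screening regression, so that selection rests on within-group association, and state the entry threshold.
- Report the change in the group coefficient when the selected measures are added (the indirect effect) with a bootstrap 95% interval, and do not judge by loss of significance.
- Omit one member of any set that sums to a constant: the four stage percentages if taken over total sleep time, and the six relative band powers if taken over their total.
- State that about one false hit per outcome is expected by chance. The group term does not cure this: the chance of at least one remains about .62 in the joint regression. Formal multiplicity control is optional in an exploratory screen.

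The cost is a few sentences in the analysis plan and a few lines of code, with no new data. The downside is that fewer sleep measures will be selected. The group term also reduces false elimination without removing it (about 4-13% remains under the significance rule), which is a further reason to report the interval.

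### The exploratory regressions of Hyperarousal Scale score on sleep measures name no group term, although entry limits on that score separate the groups, so PI-NS sleep differences can pass as hyperarousal markers

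*Combined protocol and SAP*

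**What the plan says.** Study Design/Clinical Plan sets different entry limits on the Hyperarousal Scale. PI participants must "score $\geq 29$ on the Hyperarousal Scale" and NS must "score $< 25$ on the Hyperarousal Scale". The separation is deliberate: "Our screening procedures and selection criteria are designed to allow us to identify and enroll hyperaroused PI sufferers and normally alert normal sleepers". The groups also differ by design on insomnia itself. On one side, "PI sufferers enrolled will meet Research Diagnostic Criteria for insomnia disorder", with an Insomnia Severity Index above 14; on the other, "The normal sleepers enrolled will report general satisfaction with sleep and no sleep/wake complaints".

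At the end of the analysis text in Statistical Plans, after the Aim 3 performance analyses, the plan adds bivariate correlations and multivariable regressions "to examine the association between the EEG measures and subjects' scores on the hyperarousal scale". For the regressions it states: "In regression analyses hyperarousal scores will be predicted by the various measures derived from conventional and spectral scoring of the PSG records". No group term, stratification or within-group analysis is mentioned. The next paragraph hopes that the analyses could point to sleep features "that are markers for sleep-disruptive hyperarousal and produce impairment in daytime neuro-cognitive performance", and suggests that such features might become treatment targets.

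**The concern.** The variable used to select the two groups becomes the outcome. Nobody scoring 25 to 28 is enrolled and the groups cannot overlap, so much of the spread in the score is simply PI versus NS. Any sleep measure that differs between people with insomnia and good sleepers will then correlate with the score in the pooled sample, even if it is unrelated to the score inside each group. The candidate measures include sleep onset latency, wake after sleep onset and sleep efficiency, which are themselves descriptions of insomnia.

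The design has no low-hyperarousal PI group and no high-hyperarousal NS group. The contrast between groups therefore cannot tell hyperarousal from having insomnia. At stake is the interpretation of an exploratory result: a feature of insomnia could be reported as a marker of hyperarousal and proposed as a therapeutic target.

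This is separate from using the score as a covariate in the tests of Hypotheses 1 and 2. Here it is the dependent variable.

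**Working it through.** **The plan's own figures.** There is none for these analyses. The powers in Power Considerations do reproduce with 82 per group at two-sided 0.05: .932, .869, .812, .802 and .540, against the stated .93, .87, .81, .80 and .54. The same sample size and test level are used below.

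**Inputs from the documents.** Entry limits of 29 or more and below 25; 82 + 82 = 164 participants; α = .05.

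**Assumed inputs.** The shape and spread of scores beyond the limits, and the PI-NS difference d (in SD units) on a sleep measure. The documents give neither.

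**Step 1: how much of the score's variance is group.** With equal groups, mean difference D and within-group SD s, the share is (D/2)² / ((D/2)² + s²). With whole-number scores the limits are 29 and 24. If each group's mean lies at least one SD beyond its limit, as holds for log-concave shapes, then D ≥ 5 + 2s:
- s = 3: D ≥ 11, share ≥ 30.25/39.25 = 0.77
- s = 5: D ≥ 15, share ≥ 56.25/81.25 = 0.69
- s = 6: D ≥ 17, share ≥ 72.25/108.25 = 0.67

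Under that condition the share always exceeds 0.50. Six simulated distributions gave 0.70 to 0.83: exponential and half-normal tails with s of 3 or 5, and truncated normals with untruncated means 35/20 (SD 6) and 40/18 (SD 7).

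**Step 2: the pooled correlation when there is no within-group link.** It is approximately r = √share × (d/2) / √(1 + d²/4). For share 0.78 and d = 0.5, r = 0.883 × 0.25/1.031 = 0.214. The simulated mean was 0.213.

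**Step 3: how often it is significant.** For each of the six distributions, 10,000 trials, two-sided 0.05:

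| d (SD) | pooled r | pooled, significant | with group term, significant |
|---|---|---|---|
| 0 | 0.00 | about 5% | about 5% |
| 0.2 | 0.08-0.09 | 19-22% | about 5% |
| 0.3 | 0.13-0.14 | 35-41% | about 5% |
| 0.5 | 0.20-0.22 | 75-82% | about 5% |
| 0.8 | 0.31-0.34 | about 99% | about 5% |

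**Step 4: the multivariable regression.** Statistical Plans lists 8 conventional measures plus 6 bands × 2 power measures = 20 predictors. Without a group term, using the 35/20 truncated normal, d = 0.5 and 2,000 trials per setting, each affected coefficient was significant in:
- 77% of trials when one of 20 independent predictors differed between groups
- 64% when five differed
- 37% when all 20 differed
- about 6% when all 20 differed and were mutually correlated at 0.3, because they then stand in for one another

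With a group term it was about 5% in every setting. The regression result thus depends on the joint pattern of the measures, and the firm result is the one for the simple correlations.

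**Step 5: what the group-adjusted analysis can detect.** Power ≈ Φ(atanh(r) × √(164 − 1 − 3) − 1.96). For a within-group r of 0.20 this is Φ(0.2027 × 12.65 − 1.96) = 73%; for 0.25 it is 90%. In PI alone (n = 82, √79) it is 44% and 62%. These r values are those remaining after the score has been truncated.

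**The case against.** A reader might infer that the plan will mislabel insomnia features as hyperarousal markers. The documents do not support that certainty. Pooling is not stated in so many words; it is the natural reading of analyses across subjects with no grouping named. No rule for declaring a marker is set, and the language is conditional. The marker sentence also requires a link to daytime performance, which rests on other analyses. A measure with no PI-NS difference is not affected at all. All of this stands, and it is why the point is put as can, and often would.

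The magnitudes depend on score distributions and sleep differences that the documents do not supply. That also stands, although the variance share moved only between 70% and 83% across quite different shapes.

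A pooled association is real in the sampled population; only its interpretation is confounded. This too is right, and a group term does not restore the missing comparison groups.

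A reader might also infer that only within-group associations should count. That goes too far. If scores form one continuum (assumed mean 26, SD 6) and the true correlation is 0.20, sampling at these limits gives a pooled r of about 0.23, significant in 85% of trials. The group-centred r is about 0.11, significant in about 29%. At a true 0.30, group-centred detection is about 56%, against over 99% pooled. A within-group-only rule would discard real markers.

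Exploratory status limits the consequences. It does not make a pooled correlation able to answer the question asked of it.

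**Conclusion.** The point holds as a recommended change to an exploratory analysis. The entry limits and the absence of a group term are facts of the text. Under the assumed distributions, group carries about 70-83% of the score's variance. A measure that differs by 0.5 SD between groups and has no within-group association is significant in about 75-82% of pooled correlations, against about 5% with a group term. The share would drop below half only with heavy-tailed scores that break the condition in Step 1. For the multivariable regression the problem is the same in kind but its size is not fixed by anything in the documents.

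This is more than missing detail, because a simple pooled correlation run as written cannot be told apart from a PI-NS difference. It does not show that any particular sleep measure would be wrongly named. Hypotheses 1 and 2 and the sample size do not depend on these analyses.

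**What to change.** In Statistical Plans, where the Hyperarousal Scale analyses are described:

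- Add a group term with a group-by-measure check, or run the correlations and regressions within PI and within NS.
- Report the group-adjusted or within-group estimate, with its confidence interval, beside any pooled estimate.
- Label the pooled association as confounded with insomnia status, and do not call a measure a hyperarousal marker on that association alone.
- State that the design cannot separate hyperarousal from insomnia status between groups.
- State that truncating the score within groups attenuates true associations, so a null within-group result is not evidence that a measure is not a marker.

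The cost is a few sentences of analysis text and no new data. The price in information is real: power falls, most of all within a single group, and fewer measures are likely to reach significance.
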